## **5. Specific Aims:**

**Specific Aim. Evaluate the feasibility, reliability, and clinical effects of VTS on basic tasks of motor control and on the motor symptoms of patients with movement disorders.**

Hypothesis: VTS will produce beneficial effects on basic tasks of motor control and abnormal motor symptoms in patients with movement disorders. VTS Settings will include continuous stimulation between 60-120 Hz, intermittent stimulation at  $\frac{1}{2}$  baseline step frequency during walking, and sham stimulation (2 seconds of 30 Hz stimulation only at stimulation onset).

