### **6.2 Participants:**

We will recruit 30 patients with PD who are between the ages of 18-80 years old and independently living in the community. Will additionally recruit up to 5 patients with ET and up to 5 patients with dystonia. To account for screening failures or patients who cannot tolerate the sensory stimulation, we anticipate screening and consenting ~50 individuals.

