## **7. Outcome and Statistical Approaches:**

For essential tremor and dystonia, the aims of this unblinded pilot study are to identify the optimal settings of VTS that are most promising to be tested in future clinical trials, statistical analysis will be limited to basic measures of central tendency. We will compare scores and values on the individual outcome measures listed above both on and off VTS, and within disease group means for each measure will be used to help guide the choice of settings to be tested in future studies. This pilot study will not be powered for between disease groups analysis or to test the efficacy of VTS for ET, or dystonia.

For Parkinson's disease, we expect to have data sufficient to justify exploratory statistical analysis. We have estimated that the number of patients included will allow for statistical analysis of patient's task performance before and during VTS. This was based on a medium effect size (Cohen's  $d = 0.50$ ) for the comparison of tremor power during VTS versus baseline. With an alpha of 0.05 and power of 0.80, the required sample size is 27 (based on a one-sided paired sample t-test). Thus, by recruiting 30 participants with PD, our sample size will give us sufficient statistical power to detect an effect with medium effect size. Statistical analysis will consist of a repeated measures ANOVA on the change in tasks performance scores relative to baseline. All post-hoc analyses will be corrected for multiple comparisons using Bonferroni correction.

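### Plain Bonferroni for the PD post-hoc tests is valid, but Holm's procedure would resolve more setting contrasts at the same family-wise error wherever an outcome has three or more settings (low severity)

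*Combined protocol and SAP*

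**What the plan says.** Two sentences in section 7 (Outcome and Statistical Approaches) carry the inferential plan for PD. The model: "Statistical analysis will consist of a repeated measures ANOVA on the change in tasks performance scores relative to baseline". The follow-up: "All post-hoc analyses will be corrected for multiple comparisons using Bonferroni correction". The section does not define the ANOVA factor, its levels, or which post-hoc comparisons will be made and whether they are one- or two-sided. It does not mention a sphericity test or correction, or any stepwise procedure.

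The likely factor levels come from section 5 (Specific Aims): "VTS Settings will include continuous stimulation between 60-120 Hz", plus an intermittent setting tied to step frequency during walking, plus a brief sham. The number of continuous frequencies is not stated.

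The sample size rests on a single contrast, tremor power under stimulation against its baseline value, tested one-sided with a paired t-test. Section 7 reports the result as follows: "With an alpha of 0.05 and power of 0.80, the required sample size is 27". Section 6.2 plans 30 PD patients. Section 7 calls the PD analysis exploratory.

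**The concern.** Section 6.1 says the pilot is meant to identify the best device settings. That depends on comparing settings with each other and with sham, in 30 patients. Single-step Bonferroni holds every one of *m* comparisons to 0.05/*m*. Holm does so only for the smallest p-value, and relaxes the threshold each time a hypothesis is rejected. Both keep the family-wise error at or below 0.05 without assumptions about correlation. Holm rejects everything that Bonferroni rejects and sometimes more. So where several contrasts must be resolved, the plan gives up some power.

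A secondary point concerns the omnibus test. With three or more levels, the uncorrected F test needs equal variances of all paired differences between settings. A continuous, a step-matched and a 2-second sham setting give no particular reason to expect that.

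**Working it through.** **Inputs from the documents.** PD sample size 30 (section 6.2); *d* = 0.50, alpha 0.05, power 0.80, one-sided paired t-test, required n of 27 (section 7); three kinds of setting (section 5).

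**Assumed, because the documents do not say.** Two-sided post-hoc paired t-tests; paired-difference SD of 1, so *d* is on the same scale as in the sample-size statement; the mean and covariance patterns below. Analysing change from baseline does not alter the contrasts, because the baseline cancels when two change scores are subtracted.

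**Step 1: the plan's own figure.** Power is the probability that a noncentral t with n − 1 df and noncentrality *d*√n exceeds the critical value.
- n = 27: 0.5 × √27 = 2.598, critical t = 1.706, power 0.812. At n = 26 it is 0.798, so 27 reproduces.
- n = 30: 0.5 × √30 = 2.739, critical t = 1.699, power 0.848.

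**Step 2: one Bonferroni-adjusted two-sided contrast at n = 30** (noncentrality 2.739).

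| Comparisons *m* | Threshold 0.05/*m* | Critical t | Power |
|---|---|---|---|
| 1 | 0.050 | 2.045 | 0.754 |
| 2 | 0.025 | 2.364 | 0.647 |
| 3 | 0.0167 | 2.541 | 0.583 |

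**Step 3: Holm against Bonferroni.** For *m* = 3, Holm tests the ordered p-values at 0.05/3, 0.05/2 and 0.05, stopping at the first failure. For *m* = 2 it uses 0.025, then 0.05. Each row is 40,000 simulated trials of 30 patients.

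| Scenario | Measure | Bonferroni | Holm |
|---|---|---|---|
| Two actives, each 0.5 better than sham; 2 tests versus sham | per contrast | 0.644–0.650 | 0.705–0.710 |
| | both found | 0.488 | 0.609 |
| | at least one found | 0.806 | 0.806 |
| Same means; all 3 pairwise tests | per true contrast | 0.578–0.581 | 0.614–0.615 |
| | both true differences found | 0.411 | 0.480 |
| | at least one found | 0.749 | 0.749 |
| One setting 0.5 from two equal ones; 3 pairwise tests | both true differences found | 0.411 | 0.486 |
| Graded means 0, 0.5, 1.0; 3 pairwise tests | adjacent pair | 0.580–0.583 | 0.727–0.728 |
| | all three found | 0.274 | 0.522 |
| No differences; 3 pairwise tests | family-wise error | 0.044 | 0.044 |

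The at-least-one rows cannot change, because the smallest p-value faces 0.05/*m* under both methods. With two settings there is one comparison and the methods are identical.

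**Step 4: omnibus type I error, three levels, n = 30, nominal 0.05** (40,000 trials per row).

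| Covariance pattern | Epsilon | Uncorrected | Greenhouse-Geisser |
|---|---|---|---|
| Equal SDs, correlation 0.5 | 1.00 | 0.050 | 0.047 |
| SDs 1 : 1.5 : 2, correlation 0.5 | 0.89 | 0.054 | 0.047 |
| Equal SDs, correlations 0.9, 0.5, 0.5 | 0.65 | 0.073 | 0.051 |
| SDs 1 : 1 : 3, correlation 0.5 | 0.61 | 0.076 | 0.051 |

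With two levels, sphericity holds automatically and the error is 0.050.

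**Step 5: does the omnibus inflation reach the setting claims?** With no true differences, I ran the uncorrected F test as a gate, followed by Bonferroni paired t-tests, each with its own pair's SD. At least one false setting claim occurred in 3.7% of trials at epsilon 1.00, 3.2% at 0.89 and 2.6% at 0.61. Without the gate the figures are 4.5%, 4.3% and 3.9%. All stay below 5%.

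**The case against.** The strongest reply is that nothing here is an error. Bonferroni controls the family-wise error, is easy to report, and gives simple simultaneous confidence intervals, which Holm does not. A pilot choosing settings for later trials may value an interval per setting above an extra rejection. That stands, and it means Holm is not free.

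Applicability is also uncertain. The intermittent setting is tied to walking, so tremor, Kinesia, reaction-time and dexterity outcomes may have only one continuous setting and sham. There the change does nothing, and tremor power, the only outcome that was sized, is among them. That also stands, and it limits the point to gait unless several frequencies are tested.

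A reader might infer that an uncorrected ANOVA lets through too many false claims about settings. The documents do not support this. Section 7 is silent on a sphericity correction; it does not exclude one. Step 5 shows that pair-specific post-hoc tests are not inflated, so only the omnibus p-value is exposed. Post-hoc tests using the pooled ANOVA error term would not have this protection, but the plan does not say that they will.

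Finally, Holm does not close the larger gap between sizing and analysis. The sized one-sided contrast has 85% power at n = 30; a two-sided Bonferroni contrast among three has 58%. Holm recovers about 4 of those 27 points in the three-pairwise scenario.

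**Conclusion.** The point holds as a modest efficiency improvement, not as a flaw in validity. For outcomes with three or more settings, and under the assumptions of *d* = 0.50, n = 30 and two-sided 0.05, Holm adds about 4 to 6 percentage points of power per contrast. It adds about 7 to 12 points to the chance of finding both true differences. The gain is larger if the settings are graded in effect.

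It does not raise the chance of finding at least one difference, so it would be wrong to infer that the trial becomes more likely to detect any effect of stimulation. With two settings it changes nothing.

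The sphericity point is secondary. Uncorrected omnibus error is about 5.4% under moderate variance inequality. It is about 7.5% when SDs are near 1 : 1 : 3, with a similar figure when two settings are much more highly correlated with each other than with the third. The documents give no variance data to say which applies. Severity is low, because the PD analysis is labelled exploratory.

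**What to change.** Replace the Bonferroni sentence in section 7 with:

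> Post-hoc comparisons among VTS settings within each outcome will use the Holm step-down procedure at a family-wise 0.05.

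Then list the comparisons that form each family (for example, each active setting versus sham, or all pairs) and state their sidedness. Without that list neither method can be applied unambiguously. Report unadjusted or Bonferroni intervals alongside and label them as such, since they will not always agree with the Holm decisions.

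Add a second sentence:

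> Any repeated measures ANOVA with three or more levels will use the Greenhouse-Geisser correction.

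State also that post-hoc t-tests use the SD of the pair being compared.

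The cost is a few sentences, with no extra patients, visits or data. The statistical price is the loss of simple simultaneous intervals under Holm. Greenhouse-Geisser is also slightly conservative when sphericity holds (type I error 0.047 against 0.050, and about one percentage point of power).

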## **8. Methodological Limitations and Potential Challenges:**

Potential challenges that may occur during the study include subject discontinuation prior to completion of data collection due to boredom or irritation of the skin from vibration.

Partial collected data will still be useful in helping to guide the choice of simulation

parameters in future clinical trials to test the potential of VTS as an adjunctive therapy to improve motor control or reduce the symptoms of PD, ET, or dystonia.

### **9. Data Management Plan:**

All data (including videos) collected from subjects will be stored in encrypted computer files with secure passwords. All data entered into such electronic storage files will be assigned subject ID numbers that are de-identified to ensure that all information is protected. Data will be kept in a password protected encrypted database which can only be accessed by the investigator and their staff. All data and assessments will be under the direction of the Co-PI's who will supervise research coordinators and assistants. Subject numbers will be assigned consecutively as follows:

Subjects with PD: PD1, PD2, etc. to PD30

Subjects with ET: ET1, ET2, etc. to ET5

Subjects with dystonia: DYT1, DYT2, DYT3, etc. to DYT5

De-identified data may be compared with data collected by other testing sites funded by the Parkinson's Foundation. No data that includes any HIPAA identifiers will be available to Not Impossible or to other research groups or anyone outside of the study researchers and coordinators noted in this protocol.

### **10. Possible Discomforts and Risks:**

In general, the risks are minimal for individuals who participate in this study. As the intensity of the vibration produced by the Vibrohealth device is far less than that which is produced by commercially available massagers that provide vibratory stimulation to the body, the incidence and severity of any adverse effects is expected to be limited, and no adverse events occurred in a previous trial using the Vibrohealth device in over 50 patients with PD and in our pilot testing at UF of 8 subjects. With regard to discomforts and risks, first the VTS stimulation could be annoying or unpleasant, and there is the possibility of minor skin irritation at the site where the wearable devices are placed.

Second, subjects will be asked to come to testing sessions OFF medications (as is done during standard-of-care initial clinic visits) in order to reduce confounding effects of medications, which could be temporarily uncomfortable. Third, patients may also find the tasks and scales tedious or boring. To minimize fatigue associated with completion of screening and tasks, subjects will be allowed to take frequent breaks to rest as needed. Patients will have the option of discontinuing testing at any time, and data that is partially collected may still be useful given the preliminary nature of the study. Though unlikely, it is possible skin irritation might persist outside of the testing period. Should this occur, the patient would be instructed to seek routine medical care. It is also possible that there are unknown risks for participating in this study.

#### **11. Possible Benefits:**

It is possible that VTS might temporarily improve tasks of motor control or reduce movement disorders symptoms. Subjects will also have the satisfaction of knowing that they are helping to test wearable devices that may have potential as adjunctive therapies for movement disorders in a controlled unbiased setting.

#### **12. Conflict of Interest:**

The study investigators have no conflicts of interest.

